8.1. Overview

We will conduct a Stage 1 pilot feasibility study at McLean Hospital to develop a combination of medication protocol to treat cannabis dependence in subjects with schizophrenia, schizoaffective, or any Axis I disorder. In a randomized, double-blind, placebo-controlled trial, 18 cannabis-dependent male an female subjects ages 18-45 with an Axis 1 psychiatric disorder will receive medical management (MM) over a 10-week period, with half receiving treatment with the combination of dronabinol and clonidine and half receiving placebo. Subjects will receive either the combination of dronabinol 5 mg by mouth three times daily and clonidine 0.1 mg my mouth twice daily or placebo in addition to MM over a 10-week treatment period. A follow-up visit after treatment at week 14 will evaluate the durability of treatment effects on drug use and psychosocial outcomes. Primary outcomes will include self-report of cannabis smoking and results of quantitative urine drug screens for cannabis. We also will assess cannabis withdrawal symptoms, including mood and craving. Mixed models ANOVA will be used to analyze the data.

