Safety Monitoring. The subjects will undergo the following screening procedures: a) Detailed history of cannabis use; b) Review of DSM-IV criteria for cannabis dependence; c) Review of DSM-IV criteria for schizophrenia and schizoaffective disorder; d) Medical history and concomitant medication record; e) Physical examination; f) Laboratory screen that includes CBC, electrolytes, and BUN/creatinine; g) Urine measurement of THC; h) Urinalysis and urine pregnancy test for women; i) 12lead electrocardiograph (ECG); j) urine toxicology screen; k) blood alcohol testing; l) Positive and Negative Syndrome Scale (PANSS); m) Columbia Suicide Severity Rating Scale (C-SSRS). The study physician will perform a physical examination and obtain an ECG at baseline and at 14 weeks. Laboratory data (urinalysis, blood chemistries, complete blood count, electrolytes, and liver function tests) will be done at baseline, 5, 10, and 14 weeks as well. Given that according to its labeling, dronabinol should not be taken with alcohol, sedatives, hypnotics, or other psychoactive substances because they could potentiate the central nervous system effects of dronabinol, urine toxicology and blood alcohol testing will be done weekly along with the twice weekly quantitative THC urine screens during treatment. Women of childbearing potential will have urine pregnancy tests weekly each time a urine sample is given in addition to pregnancy tests at 4 and 8 weeks during treatment; women who become pregnant will have their medication discontinued and will be referred to an obstetrician; like all subjects, they will still be followed for research visits. Suicide risk will be assessed by the physician at each MM visit.

Study Restrictions

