- 8.2.1.d. Availability and Flow of Subjects into Treatment. We plan to screen 50 subjects in the course of 20 months to achieve our desired sample size.
- 8.2.1.e. Study Visits. Following eligibility for the study (as determined by the baseline-1 visit), subjects will come to the laboratory for a baseline-2 visit to complete research assessments, provide a urine sample, and begin daily diaries and Actiwatch (see Section 8.5.2.a.) Subjects will then come to the clinic twice a week during the study medication treatment phase. One visit will include a medical visit (dispensing of pills and Medical Management; see Sections 8.3.1.b, 8.3.2) and research assessments, including a urine screen (see Section 8.5.2.a and Table 8.2). The other visit will consist only of a urine screen (see Section 8.5.2.a). After the 10-week treatment period, participants will have a follow-up assessment visit at 14 weeks. Subjects will also come in once weekly during weeks 11, 12, and 13 following the 10-week treatment period to provide a urine sample, and hand in daily diaries/actiwatch.

Subjects will be randomized to receive either dronabinol and clonidine or placebo. [name] or the research assistants will present 7 day prescriptions to the McLean pharmacy and the subject will receive blister packs containing 1 week of medication or placebo, separated into daily doses. Subjects will be asked to return unused pills at each weekly medical visit; study staff will then perform a pill count for the study record. All groups will receive capsules following the same schedule: 2 capsules three times daily for 10 weeks. Each capsule will contain either dronabinol, clonidine, or placebo. Subjects in the dronabinol-clonidine group will take 5 mg of dronabinol three times daily for 10 weeks (between 7:00-9:00 AM, 3:00-5:00 PM and 9:00-11:00 PM). Subjects in this group will also take clonidine 0.1 mg po bid (between 7:00-9:00 AM and 9:00-11:00 PM) for 8 weeks, followed by a taper to clonidine 0.1 mg po qhs for the last 2 weeks of

Partners Human Subjects Research Application Form

Version Date: July 26, 2016

the protocol. Subjects will be assessed for side effects prior to each dosing increase and the study physician will decide if increasing the dose as scheduled is appropriate. See Table 1 for a schedule of study visits.

Table 1	Cabadula	of Magazinas
i abie i	Scheaule	of Measures

Table 1 Schedule of Measures					
Measure	Baseline 1 and 2	•	_		Week 14

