- 9.1. Sample Size: In order to meet the target sample of 18, We plan to screen 50 subjects ages 18-45 in the course of 20 months to achieve our desired sample size.
- 9.2. Advertising: Subjects will be recruited via websites, newspaper advertisements, flyers on campus, word-of-mouth, and the Psychotic Division Clinical Research Core. We will not specifically recruit subjects from particular patient units at McLean. Subjects may not be inpatients at McLean at the time of their participation in the study.

9.3. Inclusion criteria Inclusion:

1) Age range 18-45 years; 2) DSM-IV diagnosis of cannabis dependence, based on the Structured Clinical Interview for DSM-IV (SCID); 3) DSM-IV diagnosis of an Axis 1 psychiatric disorder, based on the Structured Clinical Interview for DSM-IV (SCID); 4) express a desire to quit cannabis use within the next 30 days; 4) have used cannabis on 20 days within the past 30 days (i.e., an average of 5 day per week); 5) identify cannabis as their primary drug of abuse; 6) stable on antipsychotic medication for 1 month; 7) for women of childbearing age, a negative pregnancy test at screening with agreement to use adequate contraception to prevent pregnancy and monthly pregnancy tests; 8) consent for us to communicate with their prescribing clinician if one exists; 9) furnish the names of 2 locators, who would assist study staff in locating them during the study period; 10) live close enough to McLean Hospital to attend study visits; 11) plan to stay in the Boston area for the next 3 months; 12) are willing and able to sign informed consent; and 13) must be psychiatrically stable, with no psychiatric medication changes in the 4 weeks prior to their screening visit.

Partners Human Subjects Research Application Form

Version Date: July 26, 2016

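### Inclusion criterion 11 asks for 3 months' residence but the last scheduled visit is at week 14, so people who already plan to leave before that visit are eligible

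*Combined protocol and SAP*

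**What the plan says.** Section 9.3, criterion 11, requires that the subject "plan to stay in the Boston area for the next 3 months". It does not say from which day the 3 months run.

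The schedule in section 8.2.1.e runs longer. Eligibility is determined at the baseline-1 visit. After that, "subjects will come to the laboratory for a baseline-2 visit to complete research assessments". Treatment then lasts 10 weeks. "Subjects will also come in once weekly during weeks 11, 12, and 13 following the 10-week treatment period". Finally, "After the 10-week treatment period, participants will have a follow-up assessment visit at 14 weeks".

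Section 8.1 gives that last visit its purpose: "A follow-up visit after treatment at week 14 will evaluate the durability of treatment effects on drug use and psychosocial outcomes". Section 8.2.1.a adds safety measurements: "The study physician will perform a physical examination and obtain an ECG at baseline and at 14 weeks". Laboratory tests "will be done at baseline, 5, 10, and 14 weeks as well". Table 1 agrees with both.

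The Data and Safety Monitoring section refers back to the earlier safety text but places the final physical examination and ECG at 24 weeks.

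**The concern.** An eligibility rule on residence exists so that enrolled subjects can complete the schedule. This one is shorter than the schedule, so someone who says at screening that they will move away after 3 months satisfies it and is still expected to miss week 14.

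Week 14 carries data found nowhere else after treatment. The visits in weeks 11 to 13 collect only urine, diaries and Actiwatch downloads. By section 8.5.2.c and Table 1, the ASI, QIDS-SR, BAI and BIS-11 are taken after treatment only at week 14. Section 8.9 plans to analyse the ASI composites and mood episodes over treatment and post-treatment follow-up, and a subject without week 14 adds nothing to the post-treatment part. Under section 8.2.1.a and Table 1, such a subject also has no physical examination or ECG after baseline.

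**Working it through.** **Inputs**

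- Residence required: 3 months (section 9.3). By calendar start date this is 89 to 92 days, on average 91.3 days or 13.0 weeks.
- Treatment: 10 × 7 = 70 days (section 8.1).
- Last scheduled visit: 14 × 7 = 98 days from treatment start (sections 8.1 and 8.2.1.e).
- Days from screening to first dose, *s*: not stated. A separate baseline-2 visit lies in between. Assumed range 0 to 28 days.
- Sample: 18 subjects, 9 per arm (section 8.1).

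**Shortfall at week 14** = 98 + *s* − (89 to 92)

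| *s* (days) | Week-14 visit, days from screening | Days short |
|---|---|---|
| 0 (counted from first dose) | 98 | 6 to 9 |
| 7 | 105 | 13 to 16 |
| 14 | 112 | 20 to 23 |
| 28 | 126 | 34 to 37 |

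An interval of 1 to 2 weeks therefore gives a shortfall of 13 to 23 days, about 2 to 3 weeks.

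**Other parts of the schedule**

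- End of treatment is inside the 3 months when 70 + *s* ≤ 89, that is, when *s* ≤ 19 days.
- The end of week 13 (day 91) is at the boundary when *s* = 0: 91 − 92 = −1 (1 day inside) to 91 − 89 = 2 (2 days outside). With *s* = 7 it is 6 to 9 days outside.

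**Does another criterion close the gap?** Criterion 10 (living near enough to attend) has no duration. Criterion 9 (two locators) helps staff find a subject but does not require the subject to stay. Neither closes it.

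**What one loss costs.** One subject is 1/18 = 5.6% of the trial and 1/9 = 11% of an arm. For a simple comparison of two means with equal variances, the standard error is proportional to √(1/n₁ + 1/n₂):

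- 9 against 9: √(2/9) = 0.471
- 8 against 9: √(1/8 + 1/9) = 0.486, a ratio of 1.03
- 8 against 8: √(2/8) = 0.500, a ratio of 1.06

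One loss widens the week-14 standard error by about 3%, and one loss in each arm by about 6%. These are costs per loss. The documents give no rate of planned departure, so an expected loss cannot be computed.

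**If the final examination is at 24 weeks.** 24 × 7 = 168 days, so the shortfall from first dose is 168 − 92 = 76 to 168 − 89 = 79 days.

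**The case against.** The strongest case on the other side accepts the calendar gap and disputes what follows from it. Most of it stands.

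- **Bias.** A reader might infer that losses at week 14 bias the durability comparison. The documents do not support that for this mechanism. A plan to leave that exists at screening precedes randomization and cannot depend on the assigned arm. The cost is precision and missing safety measurements. With 18 subjects a chance imbalance is possible, but that is not a systematic bias.
- **Primary outcome.** A reader might infer that the primary result is at risk. The twice-weekly urine screens of section 8.5.2.a fall within the 70 treatment days, which fit inside 3 months unless screening to first dose exceeds about 19 days.
- **Role of week 14.** It is not the only follow-up. The payment text calls weeks 5, 10 and 14 all follow-up visits, laboratory tests are also taken at weeks 5 and 10, and weeks 11 to 13 supply post-treatment use data. Week 14 is the only *full post-treatment* assessment.
- **Mitigation.** Locators, the proximity criterion, $30 for each visit in weeks 11 to 13, $50 at week 14 and the commitment in section 8.9 to keep assessing dropouts all reduce the risk. They do not remove it. Criterion 11 also records an intention, so meeting it neither guarantees 3 months nor implies departure afterwards.
- **Visit window.** None is given. If week 14 meant the first day of the fourteenth week, the visit would be 91 days after first dose, on the edge of 89 to 92. Because eligibility is settled at baseline-1, that reading is also short once 2 days or more separate screening from first dose (91 + 2 − 92 = 1).
- **Cost of the fix.** Extending the period is not free. Recruitment is tight: section 8.2 expects about 50 recruited, 35 consenting and 14 to 18 randomized against a target of 18. Someone excluded for planning to leave at 3 months might have given complete 10-week data.

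**Conclusion.** The mismatch is real and small. Criterion 11 is 6 to 9 days short of day 98 if counted from first dose, and about 2 to 3 weeks short if screening to first dose takes 1 to 2 weeks, which is an assumption. No other criterion closes the gap.

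The effect is confined to the end of follow-up: fewer subjects with a post-treatment ASI, QIDS-SR, BAI and BIS-11 and, under section 8.2.1.a and Table 1, no post-baseline physical examination or ECG in those who leave. Confidence is high for the arithmetic. How many subjects would be affected is unknown. This is a worthwhile tidying of one eligibility item and does not call the trial's main result into question.

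The statement about the examination and ECG depends on which timing applies. Sections 8.2.1.a and Table 1 say 14 weeks; the Data and Safety Monitoring section says 24. The criterion is too short under either.

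**What to change.** Tie criterion 11 to the schedule, for example: *intends to remain in the Boston area through the week-14 visit (about 4 months from screening)*. Naming the visit covers any screening interval. A bare 4 months (120 to 123 days) would cover week 14 only up to 120 − 98 = 22 days between screening and first dose.

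Reconcile the 14-week and 24-week timings of the final physical examination and ECG, and match the residence period to the outcome.

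The cost is one phrase in the eligibility list and possibly a few excluded people who could have completed the 10-week treatment phase. If the sponsor would rather keep those people for the on-treatment data, the protocol should say so and accept the missing week-14 data as a known consequence.

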9.4. Exclusion criteria

1) Current diagnosis of other drug or alcohol dependence (excluding nicotine); 2) significant cardiac disease as indicated by history or suspected by abnormal ECG or history of cardiac symptoms; 3) Positive and Negative Syndrome Scale (PANSS) subscale for positive symptoms of psychosis item > 3 (moderate) at baseline evaluation; 4) current medical condition that could prevent regular study attendance; 5) liver function tests >3 times the upper limit of normal range; 6) history of seizure disorder or history of head trauma or CNS insult that could predispose the subject to seizures; 7) taking Clozapine, Wellbutrin, Mirtazapine, and/or Guanfacine; 8) current suicidal risk; 9) bradycardia less than or equal to 50 bpm, supine blood pressure of less than or equal to 100/65, a seated blood pressure of less than or equal to 90/60, or orthostatic change of >20 systolic or >10 diastolic on standing, at screening or any pre-dose assessment, or symptoms attributable to low BP (i.e. lightheadedness or dizziness on standing); 10) mental retardation or organic mental disorder; 11) currently in a residential treatment setting in which substance use is monitored and restricted, since the restricted access to drugs could represent an important confounding variable; 12) pregnant, nursing, or, if a woman of childbearing potential, not using a form of birth control judged by the investigator to be effective; 13) concomitant treatment with opioid analgesics, sedative hypnotics, or other known CNS depressants; 14) known hypersensitivity to cannabinoids or sesame oil or clonidine; 15) disease of the gastrointestinal system, liver, or kidneys that may impede metabolism or excretion of dronabinol; 16) inability to read or write in English that would hinder their ability to follow study procedures; 17) history of seizures or a family history of seizures.

Provide details of remuneration, when applicable. Even when subjects may derive medical benefit from participation, it is often the case that extra hospital visits, meals at the hospital, parking fees or other inconveniences will result in additional out-of-pocket expenses related to study participation. Investigators may wish to consider providing reimbursement for such expenses when funding is available

Subject Payments. Volunteers will receive a \$50 honorarium for attending the initial assessment interview, \$25 for baseline-2 visit, and \$50 for follow-up visits at 5, 10, and 14 weeks. They may earn \$25 for each urine sample given on a non-MM day in the first 5 weeks of the treatment and \$30 for each urine sample given on a non-MM day during the last 5 weeks of treatment. They will be compensated \$50 for the Week 1 monitoring visit and \$30 for each of three actiwatch diary UA visits at weeks 11, 12, and 13. They may also receive a bonus of up to \$100 for successful completion of all diaries. They may earn a total of \$740 for their participation in the study. Medication will be free.

A payment request will be submitted for each part of the study they finish. The research assistants will arrange for payment to be sent via mail to the subjects.

CONSENT PROCEDURES

Explain in detail how, when, where, and by whom consent is obtained, and the timing of consent (i.e., how long subjects will be given to consider participation). For most studies involving more than minimal risk and all studies involving investigational drugs/devices, a licensed physician investigator must obtain informed consent. When subjects are to be enrolled from among the investigators' own patients, describe how the potential for coercion will be avoided.

Informed consent. Eligible subjects will complete standard consent documentation. Prior to the volunteer being asked any question about his/her health, the volunteer will be given a consent form to read. The research assistant will go over

Partners Human Subjects Research

Application Form

Version Date: July 26, 2016

it in detail with the volunteer. After a physician answers any questions the volunteer may have concerning the study, he/she will be asked to provide their informed consent. If enrolled in the study, consent to communicate with their other clinicians will be obtained. Clinicians will be notified of their patients' enrollment in the study, thus allowing them to carefully monitor for changes in mood while they are undergoing treatment to stop use of cannabis.

DATA AND SAFETY MONITORING

Describe the plan for monitoring the data to ensure the safety of subjects. The plan should include a brief description of (1) the safety and/or efficacy data that will be reviewed; (2) the planned frequency of review; and (3) who will be responsible for this review and for determining whether the research should be altered or stopped. Include a brief description of any stopping rules for the study, when appropriate. Depending upon the risk, size and complexity of the study, the investigator, an expert group, an independent Data and Safety Monitoring Board (DSMB) or others might be assigned primary responsibility for this monitoring activity.

NOTE: Regardless of data and safety monitoring plans by the sponsor or others, the principal investigator is ultimately responsible for protecting the rights, safety, and welfare of subjects under his/her care.

Safety Monitoring. Dronabinol and clonidine both have been shown to have favorable safety profiles; they have been well-tolerated in several clinical trials and few adverse events have been reported. Nonetheless, we will monitor safety through the standardized methods described above in the MM visits. We will have a low threshold for obtaining additional medical workup during the study if the subject reports medical symptoms. If a subject has a clinically significant laboratory or other medical abnormality that cannot be attributed to another cause, the subject's medication will be discontinued and the subject will be followed for research visits.

As discussed above in Section 8.2.i.a, the study physician will perform a physical examination and obtain an ECG at baseline and at 24 weeks. Laboratory data (urinalysis, blood chemistries, complete blood count, electrolytes, and liver function tests) will be done at baseline and 5, 10, and 14 weeks as well. Women of childbearing potential will have urine pregnancy tests at 4, 8, and 14 weeks during the study; women who become pregnant will have their medication discontinued and will be referred to an obstetrician; like all subjects, they will still be followed for research visits.

Describe the plan to be followed by the Principal Investigator/study staff for review of adverse events experienced by subjects under his/her care, and when applicable, for review of sponsor safety reports and DSMB reports. Describe the plan for reporting adverse events to the sponsor and the McLean IRB and, when applicable, for submitting sponsor safety reports and DSMB reports to the McLean IRB. When the investigator is also the sponsor of the IND/IDE, include the plan for reporting of adverse events to the FDA and, when applicable, to investigators at other sites.

NOTE: In addition to the adverse event reporting requirements of the sponsor, the principal investigator must follow the McLean Hospital IRB guidelines for Adverse Event Reporting

Partners Human Subjects Research Application Form

Version Date: July 26, 2016

The Principal Investigator assumes responsibility for ensuring informed consent, data management, and the detection and reporting of adverse events. In general, the data to be reviewed will include screening data, baseline data, efficacy data, safety data, quality assurance data, accrual status including projections, and any other data that will help in the assessment of the effectiveness of the clinical trial.

The risk associated with participating in this study is moderate. Dronabinol has been established as a safe treatment for nausea associated with cancer chemotherapy. Clonidine is a safe treatment for hypertension. Consequently, serious side effects associated with this treatment are not expected. There will be on-call medical coverage to respond to any adverse events throughout the clinical trial.

The Principal Investigator will conduct a review of all adverse events and determine the attribution and grade of severity of the adverse event by using the following scales:

Attribution of Risk Categories:

Definite: Adverse event(s) will clearly be related to investigational agent(s) or other intervention

Probable: Adverse event(s) will likely be related to investigational agent(s) Possible: Adverse event(s) may be related to investigational agent(s)

Unlikely: Adverse event(s) will doubtfully be related to investigational agent(s)

Unrelated: Adverse event(s) will clearly not be related to the investigational agents(s)

Grades of Risk:

- 0: No adverse event or within normal limits
- 1: Mild adverse event
- 2: Moderate adverse event
- 3: Severe adverse event resulting in hospitalization or prolongation of existing hospitalization, a persistent or significant disability/incapacity, or a congenital anomaly/birth defect
- 4: Life-threatening or disabling adverse event
- 5: Fatal adverse event

Serious adverse events (SAEs) include any untoward medical occurrence that at any dose results in death or the immediate risk of death, hospitalization or the prolonging of an existing hospitalization, persistent or significant disability/incapacity or a congenital anomaly/birth defect. Subjects will be terminated from participation if the investigator feels that subjects' health or well-being may be threatened by continuation in the study. Serious unanticipated adverse events will be reported within 48 hours to the McLean Hospital IRB and NIDA. We will directly report to the FDA whenever their magnitude or frequency exceeds expectations. The principal investigator will evaluate the adverse event and determine whether the adverse event affects the Risk/Benefit ratio of the study and whether modifications to the protocol are required. In addition, he will conduct a review of all adverse events at least semi-annually, and he will evaluate the frequency and severity of the adverse events and determine if modifications to the protocol or consent form are required.

MONITORING AND QUALITY ASSURANCE

Describe the plan to be followed by the principal investigator/study staff to monitor and assure the validity and integrity of the data and adherence to the IRB-approved protocol. Specify who will be responsible for monitoring, and the planned frequency of monitoring. For example,

Partners Human Subjects Research Application Form

Version Date: July 26, 2016

specify who will review the accuracy and completeness of case report form entries, source documents, and informed consent.

NOTE: Regardless of monitoring plans by the sponsor or others, the principal investigator is ult imately responsible for ensuring that the study is conducted at his/her investigative site in accordance with the IRB-approved protocol, and applicable regulations and requirements of the IRB.

The research assistants will be responsible for day-to-day monitoring of the validity and integrity of the data. [name] will meet with the research assistants to discuss data monitoring on a monthly basis and will sample subject data folders monthly as well.

For guidance, refer to the following McLean policies:

Data and Safety Monitoring Plans and Quality Assurance

Adverse Event Reporting Guidelines

PRIVACY AND CONFIDENTIALITY

Describe methods used to protect the privacy of subjects and maintain confidentiality of data collected. This typically includes such practices as substituting codes for names and/or medical record numbers; removing face sheets or other identifiers from completed surveys/quest ionnaires; proper disposal of printed computer data; limited access to study data; use of password-protected computer databases; training for research staff on the importance of confidentiality of data, and storing research records in a secure location.

NOTE: Additional measures, such as obtaining a Certificate of Confidentiality, should be considered and are strongly encouraged when the research involves the collection of sensitive data, such as sexual, criminal or illegal behaviors.

Data Management

All data collected will be de-identified with subject ID numbers and used for research purposes only. Written records will be kept in a locked file cabinet in a locked office. They will be destroyed after 5 years. Computerized data files will also be de-identified with subject ID numbers and kept in a password protected file on a password protected computer.

To help us protect patient privacy, we have obtained a Certificate of Confidentiality From the National Institutes of Health. We can use this Certificate to legally refuse to disclose information that may identify a patient in any federal, state, or local civil, criminal, administrative, legislative, or other proceedings. The Certificate cannot be used to resist a demand for information from personnel of the United States Government that is used for auditing or evaluation of Federally funded projects or for information that must be disclosed in order to meet the requirements of the federal Food and Drug Administration (FDA).

SENDING SPECIMENS/DATA TO RESEARCH COLLABORATORS OUTSIDE MCLEAN

Specimens or data collected by McLean investigators will be sent to research collaborators outside McLean, indicate to whom specimens/data will be sent, what information will be sent, and whether the specimens/data will contain identifiers that could be used by the outside collaborators to link the specimens/data to individual subjects.

Not applicable.

Partners Human Subjects Research Application Form

RECEIVING SPECIMENS/DATA FROM RESEARCH COLLABORATORS OUTSIDE MCLEAN

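### The 0-5 adverse-event scale mixes severity with seriousness at grade 3 and places disability in both grades 3 and 4, so some severe events have no clear grade

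*Combined protocol and SAP*

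**What the plan says.** Under Data and Safety Monitoring, the principal investigator reviews all adverse events and is to "determine the attribution and grade of severity of the adverse event by using the following scales". The severity scale, headed Grades of Risk, runs from 0 (no event) to 5 (fatal).

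- Grades 1 and 2 carry one intensity word each and no descriptor. Grade 2 reads "2: Moderate adverse event".
- Grade 3 reads "Severe adverse event resulting in hospitalization or prolongation of existing hospitalization, a persistent or significant disability/incapacity", and then adds a birth defect as the third outcome.
- Grade 4 reads "4: Life-threatening or disabling adverse event".

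The next paragraph defines SAEs by outcome. It lists death and immediate risk of death, and then "hospitalization or the prolonging of an existing hospitalization, persistent or significant disability/incapacity or a congenital anomaly/birth defect".

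Two statements show what each classification is for. Expedited reporting follows seriousness: "Serious unanticipated adverse events will be reported within 48 hours to the McLean Hospital IRB and NIDA". Severity feeds the investigator's review of all events, held at least twice a year, in which "he will evaluate the frequency and severity of the adverse events and determine if modifications to the protocol or consent form are required".

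**The concern.** Severity is how intense an event is. Seriousness is whether it led to one of a fixed list of outcomes. The plan defines seriousness separately, but its severity scale turns into an outcome scale at grade 3. This leaves a gap between moderate and severe-with-a-serious-outcome, and an overlap on disability.

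The gap is realistic in this trial. Foreseeable Risks and Discomforts names hallucinations, paranoia, extreme fear and fainting among the possible side effects. Section 8.2.1.f allows a problem that needs intervention to be handled by admission, by outpatient referral or by other treatment. Two equally intense reactions could therefore be graded differently because of where they were managed.

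What is at stake is the quality of the severity record that the investigator uses when deciding whether the protocol or consent form needs to change.

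**Working it through.** The plan states no figure on this point and no arithmetic applies. The check sets the definitions side by side, classifies some cases literally, and traces where the grade is used.

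**Step 1. Compare the upper grades with the SAE definition.**

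| Outcome | Severity grade | In the SAE definition? |
|---|---|---|
| Admission or longer stay | 3, if the event is severe | Yes |
| Lasting or significant disability | 3, if the event is severe; also 4 as disabling | Yes |
| Birth defect | 3, if the event is severe | Yes |
| Life-threatening | 4 | Yes, as immediate risk of death |
| Death | 5 | Yes |
| Severe, none of the above | None fits | No |

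All three grade 3 outcomes are SAE outcomes. Nearly everything at grade 3 or above is therefore already identified as serious. What the scale does not separate is moderate from severe among non-serious events.

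**Step 2. Classify cases as the text is written.**

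- (a) Severe, not admitted, not disabling, not life-threatening, no birth defect. It fails grade 3 because none of the required outcomes occurred, and it fails grades 4 and 5. The highest grade left is 2, whose only descriptor is the word moderate.
- (b) Severe, not admitted, with significant disability. It meets grade 3 and grade 4, and no tie-break is given.
- (c) Life-threatening, managed without admission. Grade 4.
- (d) Severe and admitted, not disabling or life-threatening. Grade 3.

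Case (a) is the gap and case (b) is the overlap. Cases (c) and (d) are graded without difficulty.

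**Step 3. Trace the use of the grade.**

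- Individual stopping (section 8.3.1.b, Stopping Criteria) depends on new psychotic symptoms, pulse and blood-pressure limits, symptoms of low pressure, laboratory findings, suicidal ideation and persistence of side effects. The grade is not mentioned.
- Study-level stopping, in the same section, depends on event type and the number of subjects affected. The grade is not mentioned.
- The 48-hour report depends on an event being serious and unanticipated. The FDA sentence refers to the magnitude or frequency of such events but does not cite the scale.
- Section 8.9 plans no adverse-event analysis.
- The investigator's periodic review uses frequency and severity. This is the one stated use that the scale feeds.

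**Step 4. Look for another measure that fills the gap.** Section 8.3.2.a has a side-effect questionnaire that covers frequency, intensity and burden at the medical management visits. Nothing in the documents converts its intensity rating into a grade.

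**The case against.** The strongest reply is that little depends on the grade. The reactions of most concern have safeguards that do not use it: psychotic symptoms and low blood pressure have their own stopping criteria, and hallucinations and paranoia count by type in the study-level rule. Significant disability is an SAE under either grade, so the overlap does not alter reporting. The periodic review covers every event with no grade threshold, so an event graded 2 still reaches the investigator. Intensity is also collected by questionnaire. The adverse-event form and the hospital's reporting guidelines are not in the documents and may add detail. All of this stands, and it limits the consequence. It does not make the written scale consistent: the review relies on severity, and an investigator who grades case (a) as severe must depart from the definition.

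The documents do not support several stronger readings that a reader might infer:

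- *Severe means hospitalised.* Admission is one of three alternative outcomes in grade 3, and outpatient events that are disabling or life-threatening do rise above grade 2.
- *A mild event with a precautionary admission becomes grade 3.* Grade 3 begins with the word severe, so a mild event does not qualify. It would be an SAE by outcome and keep its low grade.
- *Severe events would drop out of a comparison between arms.* No count or rate of severe events by arm is planned, so there is no rate for a misgraded event to shift.
- *Severity is being misreported.* The text shows a risk of under-grading, not that it has happened.

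**Conclusion.** The scale is wrong as written, and the matter is minor. Grade 3 makes a serious outcome a condition of being graded severe, and disability sits in two grades. Followed literally, a severe event that is not serious, disabling or life-threatening has no grade above 2, and a severe disabling event can take either of two grades.

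The effect is limited to the recorded severity grade and to the investigator's review of frequency and severity. Participant stopping, study stopping and the 48-hour report do not depend on it. No numerical size is given, because the documents contain no expected number of such events and no analysis that uses the grade.

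The conclusion assumes that the outcomes listed in grade 3 are a requirement and not examples. The phrase *resulting in*, with no wording to mark a list of examples, supports that reading. It also assumes that no form or guideline outside these documents redefines the grades.

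**What to change.** Under Grades of Risk:

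1. Define grade 3 by intensity, that is, a severe event whether or not a serious outcome follows. A short descriptor for mild, moderate and severe would make grades 1 to 3 one consistent series.
2. Place disability in one grade only.
3. State that seriousness is classified separately, using the SAE definition already in the section, and record it as a yes/no item on the adverse-event form if the form does not have one.

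The cost is about two lines of protocol text and at most one form field. No dose, visit, stopping rule or reporting deadline changes. If events have already been graded, those recorded as grade 2, 3 or 4 should be re-graded once under the revised definitions, so that the investigator's review rests on one scale.
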